### 6.2 Extracorporeal photopheresis:

The incidence of ECP reported side effects is extremely low at less than 0.003% especially in cGVHD patient population. The procedural risks with new third generation ECP devices is even smaller. Many of the complications attributable to ECP are related to vascular access. It would be preferable to use peripheral veins, but patients with cGVHD frequently have poor veins, and alternative access must therefore be used. When central venous catheters are used, complications such as infection, clotting in the catheters, deep venous thrombosis, and vessel stenosis can occur.

For this study, modifications of ECP therapy as described below are required for patients in the first 12 weeks of study. Infection: Of note, infection during ECP+ IL-2 treatment is not considered intervention-related, since both cGVHD and the concurrent use of immune suppression medications are known risk

factors for infection. Infection is therefore considered an expected complication of cGVHD. However, patients who develop a CTC grade 3 or higher infection prior to week 12 of ECP+ IL-2 therapy will have therapy withheld during active infection. They can be considered for restarting ECP after control of infection, at the discretion of the treating physician. CVP line infection and bacteremia/sepsis requiring line removal will result in temporary stoppage of ECP therapy.

- Severe (grade-4) hematologic toxicity: ECP+IL-2 will be withheld for severe declines in peripheral counts (ANC<500, Plts<10,000) not related to malignant disease relapse, infection or other etiologies. If counts improve (ANC>1000, Plts>20,000) within 2 weeks, ECP will be restarted per schedule. If peripheral counts do not improve within 2 weeks, or drop again (ANC<500, Plts<10,000) after restarting ECP + IL-2, it will be discontinued. Use of myeloid growth factors and transfusion of platelet and PRBC's will be per standard institutional guidelines and is allowed while patients are on trial.
- Central Line associated venous thrombosis: If adequate flow volumes can be generated with clot in situ and patient has platelet counts >50,000/mm^3, patients will receive systemic anticoagulation with warfarin, enoxaparin or similar anticoagulant and ECP therapy will be continued per schedule. If, however, platelet counts are less than 50,000/mm^3, precluding anticoagulation therapy, the central line will be removed and therapeutic intervention stopped. ECP will be continued if peripheral access is available.
- Unexpected CTC Grade 3 toxicity: ECP+IL-2 will be withheld for unexpected non-hematologic toxicities that are grade 3. Expected ECP toxicities are listed in Section 8.1.4. If the toxicity resolves to grade 1 or below within 2 weeks, ECP+IL-2 can be restarted. If the toxicity does not resolve in 2 weeks to grade 1 or below, or recurs to grade 3 or above after restarting ECP+IL-2 will be discontinued.

## **7.0 Data and Safety Monitoring, Unanticipated Problems and Adverse Event Reporting**

### **7.1 Definition of Risk Level**

This is a Risk Level 3 study as defined in the [City of Hope Institutional Data and Safety Monitoring Plan](#) [policy dated 07/09/2014]. This determination was made because it is a Phase II clinical trial where the risks are at least balanced by the potential benefit to subjects and the importance of the knowledge that may result.

### **7.2 Monitoring and Personnel Responsible for Monitoring**

The Protocol Management Team (PMT) consisting of the PI, Collaborating Investigator, CRA, protocol nurse, and statistician is responsible for monitoring the data and safety of this study, including implementation of any stopping rules for safety and efficacy.

The PMT is required to submit periodic status reports (i.e., the PMT Report) according to the frequency prescribed in the [City of Hope Institutional Data and Safety Monitoring Plan](#) [policy dated 07/09/2014]. Important decisions made during PMT meetings (i.e., dose escalation, de-escalation, etc.) only need to be noted in the PMT Report submitted to the Data and Safety Monitoring Committee (DSMC).

### **Adverse Events and Serious Adverse Events**

The PI will be responsible for determining the event name, assessing the severity (i.e., grade), expectedness, and attribution of all adverse events.

**Adverse Event (AE)** - An adverse event is any untoward medical experience or change of an existing condition that occurs during or after treatment, whether or not it is considered to be related to the protocol intervention.

**Reporting** - Participating investigators will assess the occurrence of AEs and SAEs at all participant evaluation time points during the study. All CTC grade 3 or higher AEs and all SAEs whether reported by the participant, discovered during questioning, directly observed, or detected by physical examination, laboratory test or other means, will be recorded in the participant's medical record and on the appropriate study-specific case report forms from day 1 of treatment until 30 days after the last IL-2 injection.

The descriptions and grading scales found in the CTEP Version 4.0 of the NCI Common Terminology Criteria for Adverse Events (CTCAE) will be utilized for AE reporting. The CTEP Version 4.0 of the CTCAE is identified and located on the CTEP website at:

[https://ctep.cancer.gov/protocolDevelopment/electronic\\_applications/ctc.htm](https://ctep.cancer.gov/protocolDevelopment/electronic_applications/ctc.htm)

**Reporting Non-serious Adverse Events** – Adverse events will be collected after the patient is given the study treatment or any study related procedures. Adverse events will be monitored by the PMT. Adverse events that do not meet the criteria of serious OR are not unanticipated problems will be reported only in the PMT Report.

**Serious Adverse Event (SAE)** [Modified from the definition of unexpected adverse drug experience in [21 CFR 312.32](#)] - defined as *any expected or unexpected adverse events* that result in any of the following outcomes:

- Death
- Is life-threatening experience (places the subject at immediate risk of death from the event as it occurred)
- Unplanned hospitalization (equal to or greater than 24 hours) or prolongation of existing hospitalization
- A persistent or significant disability/incapacity
- A congenital anomaly/birth defect
- Secondary malignancy
- Any other adverse event that, based upon appropriate medical judgment, may jeopardize the subject's health and may require medical or surgical intervention to prevent one of the outcomes listed above (examples of such events include allergic bronchospasm requiring intensive treatment in the emergency room or at home, blood dyscrasias or convulsions that do not result in inpatient hospitalization, or the development of drug dependency or drug abuse).

**Reporting Serious Adverse Events** - begins after study treatment or any study related procedures. All SAEs occurring during this study, whether observed by the physician, nurse, or reported by the patient, will be reported according to the approved [City of Hope's Institutional policy](#) [policy effective date: 05/14/14]. Serious Adverse Events that require expedited reporting will be submitted electronically using [iRIS](#).

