### 1.2 Secondary Objectives

- Characterize and evaluate toxicities, including type, frequency, severity, attribution, time course and duration.
- Estimate overall and failure-free survival, non-relapse mortality (NRM) and relapse, through 1 year after initiation of treatment.
- Characterize chronic GVHD Symptom Scale scores -self-report (with assistance from RNs and MDs).
- Determine ongoing prednisone use with IL-2 and ECP combination therapy.
- To assess efficacy of protocol therapy ( IL-2+ECP) in helping to decrease the steroid dosage.
- Assess the immunologic effects of low-dose daily SC IL-2 + ECP.
- Correlate clinical endpoints of response with ECP performance parameters.

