#### 2.4.1.2 *Toxicity profile of IL-2 in patients with cGVHD*

The safety and immunologic activity of low-dose interleukin-2 in patients with active steroid-refractory cGVHD was assessed in a phase I trial, whose primary objective was to determine the MTD and toxicity profile of an 8-week course of IL-2. Eligibility included patients with cGVHD requiring systemic therapy that had not responded to at least 0.25 mg/kg prednisone for a 4 week period, absence of infection, and stable doses of immune suppression for 4 weeks. The study had a Phase 1 dose escalation design with 3 dose levels (0.3, 1, 3;  $\times 10^6$  IU/m^2/day for 56 days). 29 patients were accrued on protocol with subjects, 28 were evaluable for toxicity and 23 were evaluable for response. The interval between onset of chronic GVHD and initiation of IL-2 was 803 days (range, 117-2624). Patients were on a median of 3 concurrent agents (range, 1-3) for cGVHD. Skin (26 patients) and fascia (16 patients) were primary sites of involvement, but lung, liver, oral, and ocular sites were involved as well. Dose-level-C ( $3 \times 10^6$  IU/m^2/day) was declared unsafe due to constitutional side-effects (fever, malaise, and arthralgia). Dose-level-B ( $1 \times 10^6$  IU/m^2/day) was determined to be maximum-tolerated-dose in this patient population. Two patients developed dose-limiting-toxicity (thrombotic microangiopathy). CTCAE Grade IV toxicities included: TTP/HUS n=2; Dyspnea n=1, myocardial infarction n=1 and MRSA Pneumonia n=1. Grade III toxicities included induration n=3, lower GI Bleed n=1, deep vein thrombosis n=1, MRSA abscess n=1, and hemophilus bacteremia =1. Grade II toxicities included: constitutional symptoms n=1, increase in serum creatinine n=1, thrombocytopenia n=1. None experienced GVHD flare. There was no malignant disease relapse. 12/23 patients had major responses. These results suggest that low-dose IL-2 given at  $1 \times 10^6$  IU/m^2/day for 8 weeks can be administered safely in patients with active chronic GVHD.

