### **5.6 Subject Follow-Up**

While on the first twelve weeks of therapy, participants will be undergo clinical (including cGVHD) and immunologic evaluations every 3 weeks. cGVHD severity/response will be assessed using the NIH scoring criteria (see Appendix).

Toxicity assessments will be performed using the CTEP Version 4.03 of the NCI Common Terminology Criteria for Adverse Events (CTCAE) which is identified and located on the CTEP website at: [http://ctep.cancer.gov/protocolDevelopment/electronic\\_applications/ctc.htm](http://ctep.cancer.gov/protocolDevelopment/electronic_applications/ctc.htm).

If possible, adverse effects should be managed symptomatically. In the case of toxicity, appropriate medical treatment should be used (including anti-emetics, anti-diarrheals, etc.). All CTCAE grade 3 and higher adverse events experienced by participants will be collected from the time of the first dose of study treatment, through the study and until the final study visit.

Participants removed from the study for unacceptable adverse events will be followed until resolution or stabilization of the adverse event. Follow-up for participants benefiting on extended-duration therapy will continue on monthly basis in the GVHD clinic.

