### 6.1 IL-2 Therapy

The dose modifications as described below are required for patients in the first 12 weeks of study and recommended but not mandatory for participants proceeding on extended duration therapy at the end of the 12-week study.

- Unexpected CTC Grade 3 toxicity: IL-2 will be withheld for unexpected non-hematologic toxicities that are grade 3. Expected IL-2 toxicities are listed in Section 8.1.3. If the toxicity resolves to grade 1 or below within 2 weeks, IL-2 can be restarted at a 50% reduced dose that will not be re-escalated. If the toxicity does not resolve in 2 weeks to grade 1 or below, or recurs to grade 3 or above after restarting IL-2, IL-2 will be discontinued.
- Expected non-hematologic toxicity: IL-2 can be withheld and/or restarted at a 50% reduced dose for less than grade 3 toxicity (e.g. local site reactions, persistent constitutional symptoms) in the interest of patient tolerability and at the discretion of the treating physician.
- Severe (grade-4) hematologic toxicity: IL-2 will be withheld for severe declines in peripheral counts (ANC<500, Plts<10,000) not related to malignant disease relapse, infection or other etiologies. If counts improve (ANC>1000, Plts>20,000) within 2 weeks, IL-2 will be restarted at a 50% reduced dose and not re-escalated. If peripheral counts do not improve within 2 weeks, or drop again (ANC<500, Plts<10,000) after restarting IL-2, it will be discontinued. Use of myeloid growth factors and transfusion of platelet and PRBC's will be per standard institutional guidelines and is allowed while patients are on trial.
- Infection: Of note, infection during IL-2 treatment is not considered IL-2 related, since both cGVHD and the concurrent use of immune suppression medications are known risk factors for infection. Infection is therefore considered an expected complication of cGVHD. However, patients who develop a CTC grade 3 or higher infection prior to week 12 of IL-2 therapy will have IL-2 withheld. They can be considered for restarting IL-2 at their prior dose after control of infection, at the discretion of the treating physician.
- Treatment Interruption: Within the first 12 weeks of IL-2 therapy, a  $\geq 6$ -week interruption will result in the participant being considered unevaluable for response (or lack thereof), unless objective improvement of cGVHD is documented with a shorter course of IL-2.

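### Case report form entry is required only for grade 3+ events and SAEs, yet IL-2 may be held or halved below grade 3 and the toxicity objective, stopping-rule definition and severity summary have no grade floor

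*Combined protocol and SAP*

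**What the plan says.** **Collection.** Under Adverse Events and Serious Adverse Events, section 7.2 names what must be captured: "All CTC grade 3 or higher AEs and all SAEs whether reported by the participant", or found in some other way. Each such event "will be recorded in the participant's medical record and on the appropriate study-specific case report forms from day 1 of treatment"; the window closes 30 days following the final IL-2 dose. Section 5.6 sets the same threshold: "All CTCAE grade 3 and higher adverse events experienced by participants will be collected from the time of the first dose of study treatment". A later paragraph in 7.2, on non-serious events, says without a grade limit that adverse events are collected once treatment has started. It sends those that are not serious, or not unanticipated problems, to the PMT Report only.

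**Dosing.** Section 6.1 says "IL-2 can be withheld and/or restarted at a 50% reduced dose for less than grade 3 toxicity (e.g. local site reactions, persistent constitutional symptoms"), at the treating physician's discretion.

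**Use of the data.** The first secondary objective (1.2) is: "Characterize and evaluate toxicities, including type, frequency, severity, attribution, time course and duration". Section 11.2 counts as unacceptable any toxicity at least possibly related to ECP or IL-2 within 10 days of starting therapy, and that count drives the stopping table in 13.1. Section 13.2 plans to summarize observed toxicities by type, severity, onset, duration, association with treatment and outcome. None of these three places states a minimum grade.

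**The concern.** Section 6.1 treats some grade 1-2 events as important enough to interrupt or halve the study drug. Sections 5.6 and 7.2 do not require those same events to be entered on the CRF with grade, attribution and dates. If the toxicity table is built from the CRF, a non-serious grade 1-2 event that altered the delivered regimen can be absent from it.

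Two things are at stake. The first is whether the secondary objective can be met: frequency, severity, time course and duration of toxicity cannot be described below grade 3 if the events were not required to be recorded. The second is the early stopping rule. Its trigger, as defined in 11.2, includes low-grade related events, so the source of the count matters.

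**Working it through.** **Step 1: the rules side by side.**

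| Section | Role | Grade floor | Destination |
|---|---|---|---|
| 5.6 | collection | grade 3+ | not named |
| 7.2, main rule | collection | grade 3+, plus all SAEs | medical record and CRF |
| 7.2, non-serious events | collection and reporting | none | PMT Report only |
| 6.1 | IL-2 hold or half dose | acts below grade 3 | none named for the event |
| 1.2 | objective | none | – |
| 11.2 | unacceptable toxicity | none | stopping table in 13.1 |
| 13.2 | summary | none | – |

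SAEs of any grade and all grade 3+ events reach the CRF. The uncertain group is non-serious grade 1-2 events. One paragraph of 7.2 says they are collected, but none of the sections above requires a CRF entry for them, including when they change treatment.

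**Step 2: how many patients.** Inputs: 24 patients (13.1); expected rates of 10% for local reactions and 5% for constitutional symptoms (8.1.3). These are the two examples that 6.1 names.

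- Local: 24 × 0.10 = 2.4 expected; chance of at least one = 1 − 0.90^24 = 0.92.
- Constitutional: 24 × 0.05 = 1.2 expected; chance of at least one = 1 − 0.95^24 = 0.71.
- Either, no overlap: 24 × (0.10 + 0.05) = 3.6 patients.
- Either, if every constitutional case also has a local reaction: 2.4 patients.

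Grade 3 cases must be subtracted because they are recorded, and 8.1.3 foresees both grade 3 induration and fatigue of grade 3 or above. No grade split is given. Section 2.4.1.2 lists three grade III indurations among 28 phase I patients evaluable for toxicity, 3/28 = 10.7%, so a good part of the 10% local rate may already be grade 3. Nor will every remaining case lead to a dose change, since 6.1 is discretionary.

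**Step 3: the stopping rule.** The table in 13.1 was first reproduced by sequential binomial recursion, with looks at 6, 9, 12 and 18 patients and halting at 2, 3, 4 and 6 events. Cumulative stopping probabilities by 18 patients at true rates of 15%, 33% and 45% are 0.264, 0.792 and 0.956, against the stated 0.27, 0.80 and 0.95. The table therefore holds if every qualifying event is counted.

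Suppose instead that only a share f is counted, so that the effective rate is 0.33 × f:

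| f (assumed) | Probability of stopping by 18 patients, true rate 33% |
|---|---|
| 1.00 | 0.79 |
| 0.75 | 0.57 |
| 0.50 | 0.31 |
| 0.25 | 0.09 |

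The documents give no value for f. The rows show sensitivity only, and they apply only if the count is taken from data limited to grade 3+ events and SAEs.

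**The case against.** The strongest reply is that sections 5.6 and 7.2 say grade 3+ events will be recorded, not that lower grades are excluded. Section 7.2 has the principal investigator grade and attribute all adverse events. Its non-serious paragraph has no floor. The PMT, which includes the statistician and implements the stopping rules, sees those events, and the adverse event form listed in 12.1.3 has no grade limit. This stands in part. A reader might infer that low-grade events are never recorded, and the text does not support that. What remains is a conflict between rules and no requirement that these events reach the CRF.

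Second, a dose reduction should be traceable through the treatment forms (12.1.3), two-weekly dispensing in single-dose syringes with a diary of missed doses and reasons (5.2.4), and drug accountability records (8.1.4.7). This also stands. A reader might infer that many patients could run at half dose unnoticed; the documents do not support that. Nothing in these sections, though, says that these records carry the grade, attribution or resolution of the event behind a dose change.

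Third, phase I. A reader might infer that the table will miss the very symptoms that limited dose there. In 2.4.1.2 the level that "was declared unsafe due to constitutional side-effects (fever, malaise, and arthralgia") was 3 × 10^6 IU/m²/day; this trial uses 1 × 10^6, the maximum tolerated dose. The named dose-limiting toxicity was thrombotic microangiopathy. The entry "Grade II toxicities included: constitutional symptoms n=1" is not tied to a dose level, so it does not show that the limiting symptoms were below grade 3. Phase I is background only.

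Finally, a grade threshold for CRF entry is a legitimate workload choice. It is, but then the objective and summary should state that scope.

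**Conclusion.** The point holds as a conflict between collection rules and intended use. As written, non-serious grade 1-2 events that lead to an IL-2 hold or reduction may be absent from the CRF-based toxicity table, although 1.2, 11.2 and 13.2 presuppose data at all grades.

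The size is modest. About 3.6 of 24 patients would be expected to have one of the two reactions named in 6.1, assuming the rates in 8.1.3 and no overlap. The number with an event below grade 3 is smaller and cannot be derived from the documents. It would be tempting to add the thyroid and hematologic rates in 8.1.3 (5% each) and reach 25%, or 6 of 24. That sum is not supported: 6.1 does not name those categories as examples, and the total is not a true maximum either, since it leaves out thrombotic microangiopathy and all ECP toxicities.

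Any effect on the stopping rule depends on where the PMT takes its count, which the documents leave open. The primary endpoint, the two-stage decision rule and SAE capture are unaffected. The correction is worth making because the gap bears on a stated objective and is cheap to close.

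**What to change.** - **5.6 and 7.2:** reconcile the grade 3+ rule with the non-serious event paragraph. Require CRF entry, with grade, attribution, onset and resolution, for (a) any adverse event of any grade that leads to withholding, reducing or stopping IL-2 or ECP, and (b) any event that counts as unacceptable toxicity under 11.2.
- **13.2:** tabulate these events beside the grade 3+ events, together with the share of planned IL-2 dose delivered, and state which grades the toxicity summary covers.

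The cost is a few more adverse event entries per patient, with no new visit or test. The dosing rule in 6.1 stays as it is.

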### **Adverse Event Name and Severity**

The PI will determine the adverse event name and severity (grade) by using the CTCAE version 4.03. GVHD assessments by NIH consensus criteria will also be used.

**Expected Adverse Event** - Any event that does not meet the criteria for an unexpected event, OR is an expected natural progression of any underlying disease, disorder, condition, or predisposed risk factor of the research participant experiencing the adverse event.

**Unexpected Adverse Event** [\[21 CFR 312.32 \(a\)\]](#) – An adverse event is unexpected if it is not listed in the investigator's brochure and/or package insert; is not listed at the specificity or severity that has been observed; is not consistent with the risk information described in the protocol and/or consent; is not an expected natural progression of any underlying disease, disorder, condition, or predisposed risk factor of the research participant experiencing the adverse event.

### **Adverse Event Attribution**

The following definitions will be used to determine the causality (attribution) of the event to the study agent or study procedure.

**Definite** - The AE is clearly related to the investigational agent or study procedure and unrelated to any other cause.

**Probable** - The AE is likely related to the investigational agent or study procedure and unlikely related to other cause(s).

**Possible** -The AE may be related to the investigational agent or study procedure and may be related to another cause(s).

**Unlikely** -The AE is doubtfully related to the investigational agent or study procedure and likely related to another cause(s).

**Unrelated** -The AE is clearly not related to the investigational agent or study procedure and is attributable to another cause(s).

